#1. Digit Span: On each trial, a variable number of digits are presented one after another in the center of the screen. The subject’s job is to remember all the digits in the order they were presented. Between 1 and 12 digits are presented, and the subject is prompted to write down the digits he/she sees in order on the sheet, with an emphasis on accuracy.

#2. N-Back: On each trial, the subject hears a letter and sees a bluesquare somewhere on the screen. On the one-back trials, the subject presses the “A” key only if the spoken letter is the same as the one on the previous trial. Additionally, the subject presses the “L” key only if the square is in the same position as on the previous trial. The subject only has a few seconds to respond, and the emphasis is on accuracy. After a variable number of trials, the subject is asked to report whether the

letter and/or square are the same as those presented two trials back (2-back). This applies for 3-back trials, 4-back trials etc.

#3. ANT: At the beginning of each trial, the subject sees a cross in the center of the screen. The subject focuses on the cross. After a period of time, either a single blue arrow head or a group of blue arrow heads appear either above or below the cross. In the single arrow condition, the subject hits the left arrow key as quickly as possible if the arrow is pointing to the left, and the subject hits the right arrow key as quickly as possible if the arrow is pointing to the right. In the group arrow condition, the subject hits the left arrow key as quickly as possible if the center arrow is pointing to the left. The subject hits the right arrow key as quickly as possible if the center arrow key is pointing to the right. In addition to the arrows, there are either one or two blue asterisks that appear near the cross right before the onset of the arrows. In the single asterisk condition, the arrow target eventually appears in the same position as the asterisk. In the double asterisk condition, the arrow target appears either above or below the cross. The cues help the subject to respond more quickly.

#4. PIMP: At the beginning of each trial, there is a white cross in the center of the screen. Four circles appear in the corners of the screen. Each circle will contain a number of moving dots. The focus is only on the red/blue circles. After a brief duration, the four circles disappear, and a single white circle with moving dots will appear in the center of the screen. If the dots in the white circle are moving in the same direction as the dots in one of the target circles (red/blue), the subject should hit the “1” key. If the white dots are moving in a different direction than the ones from the target, the subject should hit the “2” key. There are six blocks, each lasting about 8 minutes.

#5. OSPAN: At the beginning of each trial, there is a math problem on the screen. The task is to indicate whether or not the answer to the math problem is correct. If the answer is correct, the subject should hit the left arrow key. If the answer is incorrect, the subject should hit the right arrow key. Shortly after, the math problem is replaced with a letter. The subject should remember this letter. The subject receives anywhere between 1 and 7 of these math problems and letter combinations in a row. After a variable number of math problems, the subject must write down all of the letters that he/she recalls seeing in the previous trials in the order they were presented.

#6. Filtering: On each trial, the subject sees a display of colored lines. The display appears, disappears, and reappears. The task is to determine whether the red lines changed position from the first to the second display, focusing only on the red lines. A change in the red line position is indicated by clicking the right arrow key. No change in the red line position is indicated by the left arrow key.

#7. RAPM Pre (post version for post-test): A series of patterns on the screen appear, but a piece of the pattern is missing. The subject's task is to select the piece that he/she thinks best fits the pattern by pressing the corresponding number on the keyboard. The subject has 20 minutes to complete as many patterns as possible.

3. Sub-study V: (FREQMOD) Speed of alpha oscillations and temporal resolution of perception measured with EEG

This sub-study addresses the question of whether there is a correlation between the speed of individuals' alpha oscillations (measured with EEG) and the temporal resolution of their perception. EEG data is recorded from a 60-channel cap connected to an Eximia 60-channel amplifier (Nextim, Helsinki, Finland) while subjects complete a two-flash fusion task. The task aims to determine the minimum time between two successive light flashes needed to perceive two, as opposed to one, distinct flashes. Subjects are seated 70 cm away from the monitor with a 100 Hz screen-refresh rate. Each trial begins with a central fixation cross (.98 degrees of visual angle) that reduces luminance to prepare subjects for the stimuli. The duration of the warning period is drawn from a uniform distribution between 1000 and 1500 ms. The fixation cross is present throughout the trial and the screen background is black. Grey disk stimuli are presented left or right of the fixation with equal probability and are always in the same location within a trial. Half of the trials are two-flash trials in which the first disk stimulus was present for 40 ms, followed by a blank screen of 10, 20, 30, 40 or 50 ms duration, followed by a 40 ms disk. The other half involves one-flash trials for which a single disk is presented. Subjects indicate whether they saw one or two flashes with a key press on a computer keyboard. The experiment takes 1.5 hours in total.

4. Sub-study Y: (2Back EEG) Tracking unattended memory representation in a 2-back task with EEG

This sub-study addresses the question of whether neural activity (measured with EEG) can be decoded to reveal the orientation of

objects that were briefly seen moments ago. EEG data is recorded from a 60-channel cap connected to an Eximia 60-channel amplifier (Nextim, Helsinki, Finland) while subjects complete a two-back orientation recognition task. Each block consists of serial presentation of orientation grating stimuli (set of 6 possible orientations), with subjects indicating at each presented stimulus, starting at number 3, whether it matches that shown two stimuli ago. The goal will be to decode, using multivariate pattern voxel analysis (MVPA) and inverted encoding models (IEM), the neural activity associated with each of the 6 orientations, and to identify differences in activation when the memory report is accurate versus inaccurate. The experiment will take 2 hours in total.

5. Sub-study Z: (SPACEORDEREEG)

The aim of the study is to investigate the oscillatory and representational dynamics of contextual information in visual working memory. EEG data is recorded from a 60-channel cap connected to an Eximia 60-channel amplifier (Nextim, Helsinki, Finland) while subjects complete a working memory orientation recognition task. Each block consists of serial presentation of orientation grating stimuli with subjects indicating their memory for those stimuli. The experiment will take 3-4 hours in total.

6. Sub-study AA: (SPACETIME EEG)

The aim of the study is to investigate how spatial and temporal expectation of forthcoming visual stimuli modulate both behaviour and brain oscillations. EEG data is recorded from a 60-channel cap connected to an Eximia 60-channel amplifier (Nextim, Helsinki, Finland) while subjects complete a working memory orientation recognition task. Each block consists of serial presentation of orientation grating stimuli with subjects indicating their memory for those stimuli. The experiment will take 3-4 hours in total.

7. Sub-study AB: (LTM EEG)

The aim of the study is to shed light on the working memory-long term memory transfer mechanisms. EEG data is recorded from a 60-channel cap connected to an Eximia 60-channel amplifier (Nextim, Helsinki, Finland) while subjects complete a working memory orientation recognition task. Each block consists of presentation of dot-motion stimuli with subjects indicating their memory for those stimuli. The EEG portion of the experiment will take 6-8 hours in total, split over two sessions, with an additional 1-hour behavioral session.

8. Sub-study AC: (DACOM)

The purpose of the study is to 1) investigate the trial-to-trial adaptive control of working memory in handling distraction from the discrimination stimuli, and 2) examine the neural correlates of the control processes in working memory, specifically testing the temporal and spatial characteristics of the control signal. EEG data are recorded from a Brain Products (brainproducts.com) actiCHamp Plus 64-channel high density EEG System while subjects complete a working memory dual-task paradigm. Each block consists of presentation of oriented Gabor patches, with an endogenous spatial cue indicating which of the two to memorize, and then they remember that orientation throughout the task, and recall the remembered orientation at the end of the trial. During the delay of the working memory task, another Gabor patch with varying levels of contrast will appear and participants will perform a psychophysical discrimination task on its orientation and report whether it is clockwise or counterclockwise compared to a vertical orientation. The experiment will take 3-4 hours in total.

9. Sub-study AD: (MFE)

The purpose of the study is to 1) find a neural marker of binding multiple features into VWM, and 2) investigate whether position information is an especially important feature for VWM binding. EEG data are recorded from a Brain Products (brainproducts.com) actiCHamp Plus 64-channel high density EEG System while subjects complete a typical visual working memory (VWM) task. Before memory array display, at the beginning of each trial, an arrow will be presented for 200 msec as a cue to notice either the left or right side of the memory array to be memorized. Four colored bars will be presented as the memory array then. The session will be separated into three block conditions to require participants to remember either Color and Orientation, Color and Position, or only Color in each block, respectively. At the end of each trial, one of the required features will be tested. All three blocks will be conducted with a counterbalanced order across participants. The experiment will take 3-4 hours in total.

10. Sub-study AE: (HAMS)

The purpose of this study is to find the neural mechanism whereby the irrelevant information is removed from working memory. EEG data are recorded from a Brain Products (brainproducts.com) actiCHamp Plus 64-channel high density EEG System while subjects complete a typical visual working memory (VWM) task. The participant will be required to make memory-based judgments of images in two tasks. The first task will include the presentation of three to-be-remembered oriented line patches with a memory judgment about one of the memory items after a brief delay period.

Patches may be presented sequentially or simultaneously, at the same location on the screen or at different locations across two conditions, and cued to be retained or dropped after a short delay in order to report the remembered orientation by adjusting a 180-degree dial. The second task will include the presentation of one patch and subjects will be asked to report the orientation of it after a delay. The experiment will take 4 hours total.

11. Sub-study AF: (PIII)

The purpose of the study is to investigate the ways in which prioritization of information in working memory protects its representation from interference to support more accurate behavior based on those memories. This study will test this directly both at the behavioral and neural levels. EEG data are recorded from a Brain Products (brainproducts.com) actiCHamp Plus 64-channel high density EEG System while subjects complete a typical visual working memory (VWM) task. The participant will be required to make memory-based judgments of images in two tasks. The first task will be a double-serial retrocue (DSR) task much like those typically used in the protocol's studies. The DSR task will involve the sequential presentation of two oriented patches. After a brief delay, a retrocue in the form of a digit ('1' or '2') will indicate which memory of the two oriented patches will be tested. After a longer delay of 4s, a test stimulus ('recall') will appear on the screen, which includes a line whose orientation can be adjusted by a trackball mouse to match the remembered orientation. To remind participants which item they are to recall, the retrocue digit will also re-appear on the recall display. After the participant makes their adjustment response, feedback will be provided by changing the color of the central fixation marker to green, yellow, or red, corresponding to small, mid, or large errors, respectively. Then, a second retrocue will appear that may be the same digit (50% of trials) or the other digit (50% of trials), followed by a shorter delay of 1s, and a second recall interval and feedback response. The second task will be comprised of 'neutral cue' trials that will serve as a control condition to understand the effects on performance of the meaningful retrocues. This task will be similar to the first portion of the DSR task with the sequential presentation of two oriented patches followed by a delay period. During the retrocue period, a '0' digit will appear to equate the task dynamics with the DSR task, but to be uninformative about which item will be tested. After the longer delay of 4s, the recall display will appear with a '1' or '2' digit indicating which item will be tested and the participant will make their adjustment as in the DSR task and receive feedback. At this point, the trial will end. The experiment will take 4 hours total.

8.D. tCS: includes sub-studies W and X

The sub-studies employing tCS are designed to address questions raised by the results of previous EEG studies in the lab, for example, Samaha et al., in press) and sub-study V, published as (Samaha and [name], 2015).

8.D.1.A. Behavioral tasks

1. Sub-study W: tACS study of the speed of alpha oscillations and temporal resolution of perception measured with EEG

This sub-study will replicate the procedure of approved sub-study V, using the same behavioral task. Subjects are seated 70 cm away from the monitor with a 100 Hz screen-refresh rate. Each trial begins with a central fixation cross (.98 degrees of visual angle) that reduces luminance to prepare subjects for the stimuli. The duration of the warning period is drawn from a uniform distribution between 1000 and 1500 ms. The fixation cross is present throughout the trial and the screen background is black. Grey disk stimuli are presented left or right of the fixation with equal probability and are always in the same location within a trial. Half of the trials are two-flash trials in which the first disk stimulus was present for 40 ms, followed by a blank screen of 10, 20, 30, 40 or 50 ms duration, followed by a 40 ms disk. The other half involves one-flash trials for which a single disk is presented. Subjects indicate whether they saw one or two flashes with a key press on a computer keyboard. The experiment takes 1.5 hours in total.

2. Sub-study X: tCS of 2-choice orientation discrimination with confidence ratings.

On each trial a black and white grating stimulus will appear at the center of a computer screen for a short period (33 ms). The stimulus will either be tilted to the left or to the right of vertical by 45 degrees. The subject's task is to decide whether the grating was tilted to the left or right. Following this response, they will rate their confidence in their decision on a 1-4 scale using the computer keys. The experimental manipulation is whether tCS or sham tCS is applied over occipital-parietal cortex. Subjects will complete the task under both conditions, the order of which will be counter balanced. EEG will also be recorded from 6 occipital-parietal electrode sites. Prior to this main task a short (3 min) staircasing procedure will be run in

order to titrate the contrast of the grating stimulus to achieve task performance of ~75% accuracy. Total task time will be 1 1/2 hrs, which, with an estimated 30 minutes of setup, will result in ~2 Hrs of total experiment time.

9. Inclusion and Exclusion Criteria:

9.A. Inclusion Criteria:

1. Age of \geq 18;
2. Right-handed;
3. Be in good health- determined by the investigator on basis of medical history, physical and neurological exam; for “EEG-only” sessions no physical or neurological exams will be performed;
4. Female subjects must attest to the fact that they are not pregnant on the day of the TMS procedures (by signing the relevant section of the consent form. This does not apply to “EEG-only” sessions;
6. Able to understand and speak English;
7. Able to provide written consent prior to admission.

9.B. Exclusion Criteria:

(Note: these are screened for by key personnel performing telephone screening and on-site screening (on day of the experimental session)).

1. History of epilepsy, stroke, brain surgery, cranial metal implants, structural brain lesion, devices that may be affected by TMS (pacemaker, medication pump, cochlear implant, implanted brain stimulator) (physician evaluation and medical history);
2. Women who are breast-feeding (self-report)*;
3. History of head trauma with loss of consciousness for greater than 5 minutes;
4. Any history of seizures;
5. Any family history of seizures*;
6. Diabetes requiring insulin treatment*;
7. A serious heart disorder or subjects who have had a heart attack within the last 3 months;
8. Subjects who meet DSM-IV criteria for alcohol /drug abuse problems within the last six months;
9. Any current Axis I or II diagnoses or past Axis I diagnoses;
10. Required use of medication that affects CNS function;
11. A subject with metallic implants, such as prostheses, shrapnel or aneurysm clip-S, or persons with electronic implants, such as cardiac pacemakers. The magnetic field generated by the MR

machine can cause a displacement or malfunctioning of these devices*;

12. The female subject who is pregnant or planning to become pregnant;
13. The subject has had a diagnosis of cancer in the past 3 years and/or has active neoplastic disease;
14. The investigator anticipates that the subject will be unable to comply with the protocol.
15. Prohibited Concomitant Treatment: Any investigational medication; antipsychotic, antidepressant; or ECT; Other psychotropic medications including sedative hypnotics (excluding chloral hydrate zaleplon); sumatriptan (and similar agents); anxiolytics and herbals (e.g., St. John's Wort, Kava Kava); an introduction or change in intensity of psychotherapy; any non-psychopharmacologic drug with psychotropic effects (e.g., antihistamines, beta blockers).
17. Colorblindness
18. Poor or Uncorrected vision
19. History of fainting/syncope

* Denotes criterion that does not apply to “EEG-only” sessions.

In all instances in which a subject has been excluded from participation, we will discard all data from that subject relating to the reason for exclusion.

10. Study Evaluations.

10.A. Pre-Study Screening:

The Informed Consent will be reviewed and signed prior to any study procedures being completed. Individuals currently taking a psychoactive medication, will not be allowed to enter this study. The following procedures will be completed: MRI Screening Form and Health Screening Form. Information obtained from those who fail to pass the screening will not be retained. Following these assessments, the subject will be scheduled for the experiment at HERI. A technician will conduct a follow-up interview to inquire about the subjects' comments and concerns about the experimental procedure.

10.B. Efficacy Evaluations:

N/A

10.C. Safety Evaluations:

10.C.1. Safety will be monitored by reports of adverse events, vital sign measurements and lab evaluations. HERI is staffed by medical personnel and equipped with supplies for neurological monitoring (EEG), respiratory assistance (Ambu bag, oxygen tank and mask), and management of seizure (intravenous line materials, injectable anticonvulsant medication). A physician on call will be available at all times during testing. To prevent the risk of metallic objects being propelled by the magnetic field induced by the TMS device, metallic objects will be removed from the close vicinity of the device (< 10cm), as recommended by the manufacturer. This will include removing jewelry. Watches and magnetic sensitive devices (credit cards) will be kept at least 50 cm away from the coil.

The safety procedures in this protocol were drawn from the IFCN committee recommendations and studies of the safety of TMS (Wassermann 1998) and from a study of “tolerability and safety of high daily doses of repetitive transcranial magnetic stimulation in healthy young men” (Anderson, 2006). Subjects will be screened for any history of seizure in themselves or family members (including febrile seizure), medications or conditions known to decrease seizure threshold (ETOH), implanted metallic objects or devices (e.g. pacemaker, TENS, cochlear implant, surgical clips), and any neurological or medical conditions.

10.C.2. Data Safety and Monitoring Plan

- Seizure induction is the type of adverse event that is explicitly captured under the monitoring plan; however, unanticipated adverse events that pose a serious physical risk to subjects are also included. Each *safety certified* member of the study team is responsible for alerting the PI ([name]) as soon as possible after the occurrence of a serious
 - Adverse event.
 - With regard to the “frequency of assessments/analysis of data or events captured by the monitoring plan,” this procedure is in place for each experimental session.
 - The time frame for reporting an adverse event is as soon as possible once the safety and care of the subject has been addressed.
 - The stop rule will be triggered by a single incidence of a serious adverse event.
 - Unanticipated problems or adverse events will be reported to the HS-IRB per the IRB’s posted reporting policy.
 - Adherence to the IRB-approved protocol is monitored weekly by the PI, via 1-on-1 meetings that he holds with each safety certified member of the study team who is actively running a sub-study.

10.D. Imaging: Adventitious Findings

A radiologist reviews all scans. Scans from all subjects are reviewed, although, if a study involves a series of scans within a 6-month period, only the 1st scan from a subject requires review. [name] has typically served as the radiologist overseeing the reading of scans for MRI studies. Clinically significant results will be reported to subjects no later than 37 calendar days from the day the imaging was completed (30 days for the reading of the image and 7 days are allowed from the date the image was read to contact the research participant). Subjects are given the option to have their physician informed of clinically significant findings as well.

11. References

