Written and skill testing is required. 2. Seizure identification and emergency management. (Epilepsy Foundation of South Central Wisconsin; 1.5 hour training.) The course will include education in seizure types and their typical presentations (aided by video clips); emergency management of seizures, and seizure first aid. This training will be completed with staff instructors from the Epilepsy Foundation.

These training certifications will be documented, and remain current while the personnel are involved with any of our studies. A full list of *safety certified* personnel will be a part of the “Key Personnel” list included in each Continuing Review report. Additionally, all additions to this list will be submitted to the HS-IRB via a Change of Protocol application.

In the event of a seizure or any other medical emergency during a research session, the policy will be the same as the UW Psychiatric Clinic, which operates in the same facility as our laboratory spaces. The policy states that the first response is to call 911 and administer appropriate first aid. This procedure is based upon recommendations from the Epilepsy Foundation of South Central Wisconsin and the American Red Cross. Following this, if no physician is in the room, a pre-designated physician who is in the building will be contacted.

Additionally, each of the research areas where human subjects are cared for will have postings of emergency procedures for seizures, as well as well-marked postings of emergency response numbers (e.g. 911). Additionally, a phone list for key personnel by cell phone will be available in these spaces.

8.A.3. Scanning

MRI studies will be performed on the 3 tesla MRI scanner (GE SIGNA, Milwaukee, WI) located in the Lane Family Neuroimaging Laboratory.

8.A.3.a. Positioning of the TMS coil

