Appendix A: Seizure Identification and Emergency Management

Seizure Identification

There are many different types of seizures. People may experience just one type or more than one. The kind of seizure a person has depends on which part and how much of the brain is affected by the electrical disturbance that produces seizures. Experts divide seizures into generalized seizures (absence, atonic, tonic-clonic, myoclonic), partial (simple and complex) seizures, nonepileptic seizures and status epilepticus.

Generalized – Generalized seizures affect both cerebral hemispheres from the beginning of the seizure. They produce loss of consciousness, either briefly or for a longer period of time, and are sub-categorized into several major types: generalized tonic clonic; myoclonic; absence; and atonic.

Partial – In partial seizures the electrical disturbance is limited to a specific area of one cerebral hemisphere. Partial seizures are subdivided into simple partial seizures (in which consciousness is retained); and complex partial seizures (in which consciousness is impaired or lost). Partial seizures may spread to cause a generalized seizure, in which case the classification category is partial seizures secondarily generalized.

Partial seizures are the most common type of seizure experienced by people with epilepsy. Virtually any movement, sensory, or emotional symptom can occur as part of a partial seizure, including complex visual or auditory hallucinations.

- **Simple** - People who have simple partial seizures do not lose consciousness during the seizure. However, some people, although fully aware of what's going on, find they can't speak or move until the seizure is over. They remain awake and aware throughout. Sometimes they can talk quite normally to other people during the seizure. And they can usually remember exactly what happened to them while it was going on. However, simple partial seizures can affect movement, emotion, sensations, and feelings in unusual and sometimes even frightening ways.
- **Complex** - Complex partial seizures affect a larger area of the brain than simple partial seizures and they affect consciousness. During a complex partial seizure, a person cannot interact normally with other people, is not in control of his or her movements, speech or actions; cannot control what he or she is doing; and does not remember afterwards what happened during the seizure.

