- **Non-epileptic** – Non-epileptic seizures are episodes that briefly change a person's behavior and often look like epileptic seizures. The person having non-epileptic seizures may have internal sensations that resemble those felt during an epileptic seizure. The difference in these two kinds of episodes is often hard to recognize by just watching the event, even by

trained medical personnel. But there is an important difference. Epileptic seizures are caused by abnormal electrical changes in the brain and, in particular, in its outer layer, called the cortex. Non-epileptic seizures are not caused by electrical disruptions in the brain.

Status Epilepticus

Most seizures end after a few moments or a few minutes. If seizures are prolonged, or occur in a series, there is an increased risk of status epilepticus. The term literally means a continuous state of seizure and is considered a medical emergency. Status Epilepticus is defined as 30 minutes of uninterrupted seizure activity. An estimated 42,000 deaths and thousands more instances of brain damage per year follow episodes of status. Status epilepticus is most common in the very young and the very old, with the lowest incidence at ages 15-40.

Seizure Management

Convulsive Seizure

For individuals that experience generalized seizures, the following first aid should be provided in order to assure safety for all individuals involved and nearby.

- Keep calm and reassure onlookers.
- Don't hold the person down or try to stop his movements.
- Time the seizure with your watch.
- Clear the area around the person of anything hard or sharp.
- Loosen ties or anything around the neck that may make breathing difficult.
- Put something flat and soft, like a folded jacket, under the head.
- Turn him or her gently onto one side. This will help keep the airway clear. Do not try to force the mouth open with any hard implement or with fingers. It is not true that a person having a seizure can swallow his tongue. Efforts to hold the tongue down can injure teeth or jaw.
- Don't attempt artificial respiration except in the unlikely event that a person does not start breathing again after the seizure has stopped.
- Stay with the person until the seizure ends naturally.
- Be friendly and reassuring as consciousness returns.
- Contact on-call physician.
- If, at the discretion of the physician, the subject does not require admission to a hospital, accompany him/her to his/her home to insure that he/she arrives safely.

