Non Convulsive

For individuals that experience non-convulsive, the following first aid should be provided in order to assure safety for all individuals involved and nearby.

- Watch the person carefully and explain to others what is happening. Often people who don't recognize this kind of behavior as a seizure think that the dazed person is drunk or on drugs.
- Speak quietly and calmly in a friendly way.
- Guide the person gently away from any danger, such as a steep flight of steps, a busy highway, or a hot stove. Don't grab hold, however, unless some immediate danger threatens. People having this kind of seizure are on "automatic pilot" so far as their movements are concerned. Instinct may make them struggle or lash out at the person who is trying to hold them.
- Stay with the person until full consciousness returns.
- Contact on-call physician.
- If, at the discretion of the physician, the subject does not require admission to a hospital, accompany him/her to his/her home to insure that he/she arrives safely.

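### Section 8.A.2 puts a 911 call first in any seizure, but the step lists in Appendix A omit it, do not refer back, and name only an on-call physician near the end

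*Protocol*

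**What the plan says.** Section 8.A.2 carries the protocol's emergency policy. Its scope is wide: "In the event of a seizure or any other medical emergency during a research session". It then fixes an order: "The policy states that the first response is to call 911 and administer appropriate first aid". Physician contact comes next: "Following this, if no physician is in the room, a pre-designated physician who is in the building will be contacted". The same section requires seizure procedures and emergency numbers, 911 among them, to be posted in the research areas.

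The second text is headed "Appendix A: Seizure Identification and Emergency Management". After describing seizure types it gives one list of actions for convulsive seizures and one for non-convulsive seizures. The convulsive list opens: "For individuals that experience generalized seizures, the following first aid should be provided"; the non-convulsive list opens in nearly the same way. Near the end of each comes "Contact on-call physician". Each then closes on what happens to the subject: "If, at the discretion of the physician, the subject does not require admission to a hospital, accompany him/her to his/her home".

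Section 10.C.1 adds that a physician is on call throughout testing. It does not mention 911.

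**The concern.** A person who works from the appendix alone would not meet the step that 8.A.2 puts first. The appendix is the natural text to reach for, because it is the one set out as a list of actions and its title announces emergency management.

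The event is rare, but the protocol gives it weight. Section 4.A.1 treats seizure as the main safety worry with TMS. Section 10.C.2 names it as the adverse event that the monitoring plan explicitly captures, and one serious adverse event triggers the stop rule. The protocol should therefore describe the response in only one way. What is at stake is the consistency of a safety instruction, not the validity of any estimate or test.

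**Working it through.** No figure has to be reproduced for the discrepancy itself; the check is a comparison of the texts.

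| Item | Section 8.A.2 | Appendix A, convulsive list | Appendix A, non-convulsive list |
|---|---|---|---|
| 911 call | Yes, as part of the first response | Not mentioned | Not mentioned |
| First aid | Yes, alongside the 911 call | Yes, itemised | Yes, itemised |
| Which physician | Pre-designated, in the building, if none is in the room | On-call | On-call |
| Place of the physician contact | After the 911 call and first aid | After staying until the seizure ends | After staying until full consciousness returns |
| Hospital or home | Silent | Physician's discretion | Physician's discretion |
| Reference to the other text | None | None | None |

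Four things follow.

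1. **Omission.** 911 appears in 8.A.2 twice, as the first response and as an example of a posted number. It appears nowhere in Appendix A. The appendix itself classes status epilepticus as a medical emergency, and 8.A.2 covers any medical emergency, but neither list links back to that policy.
2. **Sequence.** In 8.A.2 the first call for help is made at the outset. In each appendix list the only call comes near the end. The bullets are not numbered, so this order is inferred from their position.
3. **Agreement.** Both texts put physician contact after first aid, so on that step they do not conflict.
4. **Identity of the physician.** Section 8.A.2 describes someone designated beforehand and present in the building. Appendix A and 10.C.1 describe someone on call. Nothing says whether these are one role or two.

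**Scope.** The title page lists sub-studies L.3, O, Y, AA, AC, AD and AE under this NCT number. Section 8.C places all of these except L.3 among the EEG-only studies, so TMS arises only in L.3. Section 7 plans 24 subjects for L.3, and section 6 gives two to three TMS/EEG sessions each:

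- 24 × 2 = 48 sessions at the least
- 24 × 3 = 72 sessions at the most

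In the umbrella protocol the TMS sub-studies are L.3, M.1, M.2, T.1 and T.2:

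- 5 × 24 = 120 planned subjects
- 17 + 2 = 19 from M.1 and M.2 completed under the previous protocol
- 120 − 19 = 101 remaining

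**The case against.** The strongest reply is that the texts fit together. The policy in 8.A.2 has two parts, the 911 call and first aid, and both appendix lists are introduced as first aid. On that reading the appendix only fills in the second part. It never tells staff to call the physician instead of 911, and it never claims to be complete. In addition, a safety-certified team member trained in first aid and seizure management must be in the room for all TMS procedures, so nobody is expected to act from the appendix alone.

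Part of this stands. A reader might infer that the protocol contains two rival procedures, or that the appendix replaces the 911 call with a call to a physician. The text does not support that: it is silent on 911 and excludes nothing. A reader might also take the closing step on hospital or home as a contradiction of 8.A.2. It is not one, because 8.A.2 has no rule on disposition, and a physician's decision on admission is compatible with an earlier 911 call.

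The reply does not remove the discrepancy. The lists go beyond first aid: they say whom to contact and how the subject leaves. A list that includes notification, but leaves out the notification that the policy places first, is inconsistent with that policy. The training requirement lowers the chance of an error, but it does not align the texts.

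**Conclusion.** The point holds as an inconsistency of omission and sequence between 8.A.2 and Appendix A, with an unresolved question of whether the two descriptions of the physician mean the same person.

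Its reach in this trial is L.3: 24 planned subjects and 48 to 72 TMS/EEG sessions if all attend as planned. The umbrella figure of up to 120 subjects might be taken as the size of the problem here, but M.1, M.2, T.1 and T.2 are not listed under this NCT number. L.3 uses single-pulse TMS, for which section 4.A.1 reports no seizures in normal volunteers, so the procedure is unlikely to be needed.

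It might also be inferred that the posted procedures repeat the appendix and share its gap. The protocol does not show the postings or say which text they follow, so that can only be checked.

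The conclusion rests on reading the appendix bullets in the order printed. It has no bearing on sample size, error rates or analysis. It merits correction because it concerns subject safety and costs almost nothing to put right. Which procedure is clinically right is not judged here.

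**What to change.** Reconcile section 8.A.2, section 10.C.1 and Appendix A so that they give one sequence, stating who is called and at what point. Use one term for the physician, or define two roles if two are meant. Have 8.A.2 and Appendix A refer to each other. Then compare the posted seizure procedures with the agreed text and re-issue them only if they differ.

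The content of the sequence is for the investigator and the responsible physicians to decide. The cost is a short protocol amendment and a check of the postings; no data collection or analysis changes.
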